9.4. Reporting period

Details of the targeted AEs will be documented and reported from the date of randomisation until 15 days post last IMP administration. If the patient has suffered an AE within the 15 days post last IMP administration then the information should be documented on the relevant forms and patients medical notes.

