7. TRIAL TREATMENT / INTERVENTION

7.1. Treatment(s) and Dosing Schedule

The intervention is a therapeutic dose of Cholecalciferol (Oleovit D3 or vitamin D3) versus placebo in an otherwise identical oily solution of MCT, either given by nasogastric or jejunal feeding tube or swallowed. We will use the preparation that is commercially available in Europe (Cholecalciferol, 12.5ml per bottle, 400IU per drop, total dose of 180,000IU per bottle):

- Vitamin D: oral/enteral pharmacological dose of cholecalciferol (vitamin D3)
 - Loading dose of 540,000IU (dissolved in 37.5ml of MCT) followed by 4000IU daily (10 drops) for the entire active trial period (90 days) – total dose 900.000IU
- Placebo: identical regime
 - Loading dose of 37.5ml MCT followed by 10 drops daily

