8. OUTCOME MEASURES AND TRIAL PROCEDURES

Screening - Day -3 to 0

- Vitamin D analysis
- Eligibility
- Informed consent

Please note, details of the screening assessment have been described earlier in Section 6.2.

Baseline - Day 0

The patient receives the loading dose of the allocated intervention (vitamin D or placebo) and the following is recorded.

- Age
- Sex
- ICU admission diagnosis
- ICU type (medical, surgical, neurological, cardiac)
- Charlson comorbidity index (based on co-morbidities on ICU admission)
- Simplified Acute Physiology Score (SAPS III)
- Therapeutic Intervention Scoring System (TISS 28)
- SOFA score (on admission to ICU)
- Number of organ failures
- Katz Activities of Daily Life (prior to ICU admission)
- Serum calcium
- If applicable¹, patient health-related quality of life questionnaire (EQ-5D-5L and WHODAS 2.0, proxy if patient does not have capacity)
- If applicable², blood sample for future research (pre-intervention)

Please note, if there has been a >24-hour delay since eligibility was confirmed, eligibility must be re-assessed prior to the patient receiving the loading dose.

Please note, the day of the study medication loading dose is the start for the calculation of the time dependent outcome data.

The SOFA and SAPS III scores will also capture data on the presence of sepsis and renal dysfunction (our 2 predefined sub-groups).

Day 1

The patient begins daily dose treatment with allocated intervention for 90 days.

Day 5

- Survival status
- Serum calcium
- Treatment with allocated trial medication
- Trial medication compliance
- SOFA score and type(s) of organ support
- Presence of sepsis/infection
- Targeted adverse events (refer to Section 9.3.2)
- If applicable², blood sample for future research

Day 12

• If applicable², blood sample for future research

Day 28

- Survival status (primary endpoint 28-day mortality)
- Serum calcium (if still in hospital)
- Targeted adverse events (refer to Section 9.3.2)
- Treatment with allocated trial medication
- Trial medication compliance
- If applicable¹, patient health-related quality of life questionnaire (EQ-5D-5L and WHODAS 2.0, proxy if patient does not have capacity)
- If applicable¹, health economics questionnaire

Day 90

- Survival status
- · Katz Activities of Daily Living
- Targeted adverse events (including self-reported infections requiring antibiotics, self-reported falls and fracture, hospital, and ICU admissions)
- Discharge destination

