- Trial medication compliance
- If applicable¹, patient health related quality of life (EQ-5D-5L and WHODAS 2.0, proxy if patient does not have capacity)
- If applicable¹, health economics questionnaire

Day 90 marks the end of the trial intervention.

1 year

- Survival status
- If applicable¹, patient health related quality of life (EQ-5D-5L and WHODAS 2.0, proxy if patient does not have capacity)
- If applicable¹, health economics questionnaire

Information obtained at day 28, 90 and 1 year (see above) can be obtained from the hospital's data management systems or via telephone interview with the trial patient or delegated family member. Additional information will be obtained from reviewing hospital clinical records and via NHS Digital and if applicable¹, patient Health economics questionnaire.

The following questionnaires will not be collected for patients recruited post substantial amendment 5 (SA5) implementation:

- EQ-5D-5L
- WHODAS 2.0
- Health economics questionnaire

¹ Only applicable if patient recruited pre-SA5 implementation

² Only applicable if patient recruited pre-SA5 implementation and consents to the sub-study

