8.2. Secondary Outcomes

- 90 day and 1-year mortality
- ICU and hospital mortality
- Hospital and ICU length of stay (starting at day 0, ending at discharge from the trial site or day 90 or mortality, whichever occurs first)
- Change in organ dysfunction on day 5 as measured by Sequential Organ Function Assessment score (SOFA), number of organ failures (0-6; defined as > 2 SOFA points in each of the 6 categories)
- Hospital and ICU readmission until day 90
- Discharge destination (home, rehabilitation, other hospital)
- Katz Activities of Daily Life at day 90
- Self-reported infections requiring antibiotics until day 90
- Health-related quality of life (EQ-5D-5L) at 90 days and 1 year¹
- Disability assessment (WHODAS 2.0) at 90 days and 1 year¹
- Secondary health care utilisation in the first year (ICU and hospital length of stay, readmissions and utilisation of hospital and community care resources after hospital discharge 1 year after randomisation), from Hospital Episode Statistics, civil registry data held by NHS Digital and patient questionnaires¹
- Health economics analysis¹
 - Cost effectiveness of screening for and treating VDD in critical illness
 - Cost per quality-adjusted life year gained 1 year after randomisation and at end of life

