8.4. Safety outcomes

Hypercalcaemia at day 5

- Self-reported falls, fractures until day 90
- New episodes of kidney stones

¹ UK-specific outcome no longer collected for patients recruited post-SA5 implementation

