8.5. Schedule of Assessment

ASSESSMENT	Screening	Enrolment Baseline	Begin Daily Dose	Follow-Up	Follow-Up	Follow-Up	Follow-Up	Follow-Up
ASSESSMENT	Day -3 to Day 0	Day 0	Day 1	Day 5	Day 12	Day 28	Day 90	Month 12
Time window (days)				±2	±2	+4	±14	±30
25(OH)D	Х							
Eligibility assessment	X	X						
Informed consent	X	X						
Randomisation		X						
Baseline demographics		Х						
SAPS III		Х						
TISS 28		X						
Charlson comorbidity index		Х						
Adverse events								
Mortality ¹				Х		X ²	Х	Х
Serum calcium	Х	Х		Х		X3		
Falls							X	
Fractures							X	
New episodes of nephrolithiasis							X	
Number of organ failures ¹		Х		Х				
Infections requiring antibiotics ¹							Х	
Hospital and ICU readmission ¹							X	
Intervention								
Loading dose 540,000 IU or matched placebo		Х						
Daily dose 4,000 IU or matched placebo			X	Х	X	Х	Х	
Outcome measures								
SOFA		Х		Х				
qSOFA		Х						
Discharge destination							Х	
Katz Activity of Daily Living		Х					Х	
NHS digital, ONS/HES data								Х
(vitamin D metabolic profiling (optional research)		X ⁴		X ⁴	X ⁴			
UK specific outcomes								
Health related quality of life (proxy EQ-5D-5L)		X ^{5,6}				X ^{5,6}	X ^{5,6}	X ^{5,6}
Health related quality of life (EQ-5D-5L)		X ⁵				X ⁵	X ⁵	X ⁵
Disability assessment (proxy WHODAS 2.0)		X ^{5,6}				X ^{5,6}	X ^{5,6}	X ^{5,6}
Disability assessment (WHODAS 2.0)		X ⁵				X ⁵	X ⁵	X ⁵
Health economics questionnaire						X 5	X ⁵	X5

¹ Outcome measure ² Primary outcome ³ If still an inpatient

 $^{^4}$ If patient recruited pre-SA5 implementation and consents to the sub-study 5 If patient recruited pre-SA5 implementation 6 To be used if the patient does not have capacity

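### The Day 90 contact may fall up to 14 days before Day 90, so outcomes counted to day 90 can be under-recorded, and after a full course no scheduled contact reaches the end of the targeted adverse-event period

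*Protocol*

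**What the plan says.** **Treatment period.** Protocol section 8, under Day 1: "The patient begins daily dose treatment with allocated intervention for 90 days". The same section adds: "Day 90 marks the end of the trial intervention". Section 7.1 describes the loading dose as "followed by 4000IU daily (10 drops) for the entire active trial period (90 days") and gives a course total of 900,000 IU.

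**Outcomes counted to day 90.** Section 8.2 lists "Self-reported infections requiring antibiotics until day 90", and hospital and ICU readmission over the same period. Section 8.4 lists "Self-reported falls, fractures until day 90". New kidney stones carry the day 90 limit in the Trial Summary; section 8.4 lists them without a limit. Section 14.2 defines compliance as the self-reported share of doses taken up to day 90 and requires more than 80% for the per-protocol population.

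**Contact schedule.** In section 8.5, the row beginning "Time window (days" gives ±2 for Day 5, ±2 for Day 12, +4 for Day 28, ±14 for Day 90 and ±30 for Month 12. Falls, fractures, nephrolithiasis, infections and readmissions are marked only in the Day 90 column. The text of section 8 also lists targeted adverse events and compliance at Day 5 and Day 28. At 1 year it lists survival status, plus questionnaires for patients recruited before SA5.

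**Adverse-event period.** Section 9.4: "Details of the targeted AEs will be documented and reported from the date of randomisation until 15 days post last IMP administration". Section 9.3.1 uses the same period. Section 9.4 continues: "If the patient has suffered an AE within the 15 days post last IMP administration then the information should be documented on the relevant forms".

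**The concern.** The contact that closes the day 90 outcomes is allowed to take place before day 90. A site that telephones on Day 76 complies with the schedule, but it cannot learn about the remaining 14 days of events or doses, and no later contact is planned to ask. Observation time for these outcomes would then depend on when each site calls.

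A second mismatch concerns safety. The targeted adverse-event period is tied to the last dose. For a patient who takes the whole course it runs past the latest day on which the Day 90 contact may be made.

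At stake are the completeness of several secondary and safety outcomes and the meaning of the per-protocol set. A later analysis plan cannot repair this, because it concerns what is collected.

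**Working it through.** **1. Last planned dose.** Inputs from sections 7.1 and 8: loading dose 540,000 IU on Day 0, then 4,000 IU daily for 90 days from Day 1.
- Course total: 540,000 + 90 × 4,000 = 900,000 IU, which equals the stated total. There are therefore 90 daily doses.
- Last dose: 1 + 90 − 1 = Day 90.

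**2. Contact window.** Section 8.5: 90 − 14 = Day 76 to 90 + 14 = Day 104, or 29 possible days.

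**3. Shortfall for the day 90 outcomes.**
- Earliest contact: 90 − 76 = 14 days missed, and 14/90 = 15.6%.
- Contact on or after Day 90: none missed.

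**4. Average loss, under an assumption.** The protocol does not say how calls are spread over the window. If they were spread evenly:
- share before Day 90: 14/29 = 48.3%
- mean loss among these early contacts: (1 + 2 + … + 14)/14 = 105/14 = 7.5 days
- mean loss per contacted survivor: 105/29 = 3.6 days, or 4.0% of 90 days.

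The possible range is 0 days (every call on or after Day 90) to 14 days (every call on Day 76).

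**5. Compliance.** By Day 76 at most 76 of the 90 daily doses can have been taken: 76/90 = 84.4%. If doses not yet due counted as not taken, four missed doses would give 72/90 = 80.0%, which does not exceed 80%. If they did not count, compliance from the contact to day 90 would be unverified.

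**6. Targeted adverse-event period.** For a last dose on day L the period closes on L + 15, so the contact must be on or after L + 15 to cover it.

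Full course (L = 90): closes on Day 105.

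| Contact day | Days of the period still open |
|---|---|
| 76 | 29 |
| 90 | 15 |
| 104 | 1 |

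Earlier stopping: a contact on day C covers the period if L ≤ C − 15.

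| Contact day | Covers the period if the last dose was by |
|---|---|
| 76 (so any in-window day) | Day 61 |
| 90 | Day 75 |
| 104 | Day 89 |

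**7. Later contacts.** Month 12 ± 30 days collects survival and, for patients recruited before SA5, questionnaires. Of the targeted events in Table 1 of section 9.3.2, only mortality is picked up there.

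**The case against.** A reader might infer that the Day 90 contact always precedes the close of the adverse-event period. It does not. The period follows the last dose, and sections 7.5 and 7.6.3 foresee treatment ending early. For those patients an in-window contact can cover it. Even for a completer contacted on Day 104 the gap is one day.

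A reader might also infer that the tail is outside reporting, or that the protocol cannot meet its own period. Section 9.4 tells sites to document events in those 15 days. Section 9.3.2 puts hypercalcaemia, nephrolithiasis, falls and fractures on a separate Adverse Events Form, and expedited SAEs are reported within 24 hours of the site becoming aware, whatever the visit. A reporting period that outlasts the last visit is not in itself a contradiction. This stands. What is missing is a scheduled prompt. Infections are the weakest case, since Table 1 assigns them to the Day 90 Form alone.

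Nor is Day 90 the only collection point: section 8 lists targeted events and compliance at Day 5 and Day 28. But those contacts cannot see the weeks before Day 90. Section 8 also allows hospital systems, clinical records and NHS Digital as sources. These can recover readmissions, and fractures or stones treated in hospital, but not reliably self-reported falls or infections treated in the community.

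One might argue that the lost days matter most because cumulative exposure is then highest. This is weak: by Day 76 a fully dosed patient has had 540,000 + 76 × 4,000 = 844,000 IU, or 93.8% of the total.

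Finally, the trial is double-blind and randomisation is stratified by site, so call timing should not differ by arm. That also stands.

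**Conclusion.** The point holds in a limited form. An in-window contact on Days 76–89 can miss up to 14 of the 90 days (15.6%) by which these outcomes and compliance are defined, and no later scheduled contact asks about them. The loss is mainly in self-reported falls and fractures and in community-treated infections. For patients who take the full course, the targeted adverse-event period ends on Day 105, 1 to 29 days after any permitted Day 90 contact.

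The 14-day maximum and the Day 105 against Day 104 comparison follow from the protocol's own figures. The 48% and 3.6-day averages rest on an assumed even spread of calls and are only illustrative.

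A reader might infer that the treatment comparison is biased. The protocol does not support that: the expected effect is under-counting and unequal observation time in both arms. The primary outcome does not depend on this contact, and the mortality outcomes have their own follow-up. The matter deserves correction because it affects several secondary and safety outcomes and the per-protocol set, and because the remedy is cheap.

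**What to change.** 1. In section 8.5, make the Day 90 window one-sided, not before Day 90, for example 0/+14 days. Day 28 already has this form (+4).
2. For the outcomes with a day 90 limit, count events dated up to Day 90, so that later contacts do not lengthen the observation period. Confirm that the forms hold a date for each readmission, infection, fall, fracture and stone; the forms are not shown, so they may do so already.
3. Reconcile section 8.5 with sections 9.3.1 and 9.4. A 0/+14 window alone still ends on Day 104 and leaves 1 to 15 days of the period uncovered after a full course. Two options are a hospital-record check for targeted events up to 15 days after the last dose, or asking the adverse-event question at or after that date.

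The cost is one cell in the schedule, a check of the date fields and a note to sites. The drawback is a narrower window (15 possible days instead of 29) and slightly later Day 90 assessments: if calls were spread evenly over Days 90–104, Katz would be taken at a mean of (90 + 104)/2 = Day 97.

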9.5. Reporting procedure – at site

[figure not shown]
9.5.1. Adverse Events

The safety profile of the IMP used in this trial is well characterised, therefore only the expected AEs described in Section 9.3.2 should be reported to the VITDALIZE UK Trial Office. However, all AEs should be documented in the source data.

9.5.2. Serious Adverse Events

Sites should report SAEs which are NOT classed as 'protocol exempt' or those that can be reported in non-expedited manner (as defined in Sections 9.3.1 and 9.3.2), to the VITDALIZE UK Trial Office within 24 hours of site being made aware of event.

Table 2: Reporting SAEs

On becoming aware that a patient has experienced a SAE, the PI or delegate should report the SAE to their own Trust in accordance with local policies and to the VITDALIZE UK Trial Office in accordance with the VITDALIZE UK Protocol. In addition, the research team at site will be required to respond to any related queries raised by the VITDALIZE UK Trial Office as soon as possible.

The PI (or medically qualified delegate) will assess relatedness and severity of the SAE. The following categories will be used to define the relatedness (causality) of the SAE:

Category	Definition	Causality
Definitely	There is clear evidence to suggest a causal relationship, and other possible contributing factors can be ruled out	
Probably	There is evidence to suggest a causal relationship, and the influence of other factors is unlikely	Related
Possibly	There is some evidence to suggest a causal relationship, however, the influence of other factors may have contributed to the event (e.g. the patient's clinical condition, other concomitant events or medication)	
Unlikely	There is little evidence to suggest there is a causal relationship; there is another reasonable explanation for the event (e.g. the patient's clinical condition, other concomitant events or medication)	Unrelated
Not related	There is no evidence of any causal relationship	

To report an expedited SAE to the VITDALIZE UK Trial Office, the PI or delegate must complete, date, and sign the trial specific VITDALIZE UK SAE forms. The completed form should be uploaded on the eCRF and sent to the VITDALIZE UK Trial Office using the contact details listed below as soon as possible and no later than 24 hours after first becoming aware of the event:

Completed SAE Forms can be sent to the VITDALIZE Trial Office on:

Via email: [contact]

On receipt of a SAE Form, the VITDALIZE UK Trial Office will assign the SAE a unique reference number and return this via email to the site as proof of receipt. If the site has not received confirmation of receipt of the SAE from VITDALIZE UK Trial Office or if the SAE has not been assigned a unique SAE identification within 1 working day, the site should contact the VITDALIZE UK Trial Office. The site and the VITDALIZE UK Trial Office should ensure that the SAE reference number is quoted on all correspondence and follow-up reports regarding the SAE and filed with the SAE in the Site File.

Following reporting of a SAE, the patient should be followed up until resolution or stabilisation of the event. Follow-up information should have the SAE reference number provided by the VITDALIZE UK Trial Office and be recorded as follows:

- Updating the information via the eCRF
- Completing a new paper SAE form with the follow-up information

Once the SAE has been resolved, all follow-up information has been received and the paperwork is complete, the **original paper SAE form** that was completed at site must be returned to the VITDALIZE UK Trial Office and a copy kept in the Site File.

9.6. Reporting Procedure – BCTU Trials Office

Proof of receipt will be provided to the site within 1 working day. The SAE reference number will be quoted on all correspondence and follow-up reports regarding the SAE and filed with the actual SAE in the TMF.

On receipt of an SAE Form, the CI or delegate will determine the seriousness and causality of the SAE. An SAE judged by the CI or delegate(s) to have a reasonable causal relationship with the trial medication will be regarded as a Serious Adverse Reaction (SAR). The causality assessment given by the PI will not be downgraded by the CI or delegate(s). If the CI or delegate(s) disagrees with the PI's causality assessment, the opinion of both parties will be documented, and where the event requires further reporting, the opinion will be provided with the report.

The CI or delegate(s) will also assess all expedited SAEs for expectedness. If the event meets the definition of a SAR that is unexpected (i.e. is not defined in the approved version of the Reference Safety Information (RSI): Section 4.8 Undesirable Effects - Summary of Product Characteristics (SPC) Cholecalciferol – Oleovit D3 14,400 IU/ml oral drops, solution, December 2015 it will be classified as a Suspected Unexpected Serious Adverse Reaction (SUSAR).

9.7. Reporting to the Competent Authority and Research Ethics Committee

9.7.1. Suspected Unexpected Serious Adverse Reactions

BCTU will report a minimal data set of all individual events categorised as a fatal or life threatening SUSAR to the Medicines and Healthcare products Regulatory Agency (MHRA), REC and Sponsor within 7 days. Detailed follow-up information will be provided within an additional 8 days.

All other events categorised as non-life threatening SUSARs will be reported within 15 days.

9.7.2. Serious Adverse Reactions

The Sponsor will prepare report details of all SAEs (including SUSARs) for the MHRA and REC annually from the date of the Clinical Trial Authorisation, in the form of a Development Safety Update Report (DSUR). The reports will be sent to the MHRA and REC by the National Co-ordinating Centre (NCC) on behalf on the Sponsor.

9.7.3. Adverse Events

Details of all AEs will be reported to the MHRA on request.

9.7.4. Other safety issues identified during the course of the trial

The MHRA, REC and Sponsor will be notified immediately if a significant safety issue is identified during the course of the trial.

9.8. Investigators

Details of all SUSARs and any other safety issue which arises during the course of the trial will be reported to Pls. A copy of any such correspondence should be filed in the Site File.

9.9. Data Monitoring Committee

The independent Data Monitoring Committee (DMC) will review all SAEs.

9.10. Reporting to Third Parties

All SAEs will be reported to the Sponsor, who will be responsible for reporting SAEs and trial related progress to the manufacturer of the Investigational Medicinal Product (Fresenius Kabi) in line with their contractual requirements.

10. DATA HANDLING AND RECORD KEEPING

10.1. Source Data

Source data is defined as all information in original records and certified copies of clinical findings, observations, or other activities in a clinical trial necessary for the reconstruction and evaluation of the trial. To allow for the accurate reconstruction of the trial and clinical management of the subject, source data will be accessible and maintained.

For the eCRF, sites will be provided worksheets which can be used to capture source data. In situations where sites do not use worksheets, source data should be kept as part of the patients' medical notes generated and maintained at site (Please refer to Tables 3 and 4).

Table 3: Source Data

Data	Source		
Patient Reported Data (EQ-5D-5L; WHODAS 2.0)	The completed paper form is the source and a copy will be forwarded directly to the VITDALIZE Trial Office.		
Laboratory results	The original lab report, which may be electronic, is the source data and will be kept and maintained, in line with normal local practice. Worksheets will be provided that can be used to document lab results. In situations where these are used, will be source data.		
Clinical event data	The original clinical annotation is the source data. This may be found on clinical correspondence, or electronic or paper patient records. Clinical events reported by the patient, either in or out of clinic (e.g. phone calls), must be documented in the source data. Worksheets will be provided that can be used to document lab results. In situations where these are used, will be source data.		
Health economics (resource use) data	This will be completed on the Health Economics (resource use) CRFs via interview or telephone with the patien and/or legal representative. The completed paper form is the source and a copy will be forwarded directly to the VITDALIZE Trial Office.		
Recruitment	The original record of the randomisation is the source. It is held on the Medical University of Graz eCRF servers as part of the randomisation and data entry system.		
Withdrawal	Where a participant expresses a wish to withdraw, the conversation must be recorded in in the source data.		

